2 LIST OF ABBREVIATIONS

AE	Adverse Event
BE	Bioequivalence
CRF	Case Report Form
CRO	Contract Research Organization
CV	Coefficient of Variation
DD	Drug Dictionary
EAW	External Anogenital Warts
eCRF	Electronic Case Report Form
EOS	End of Study
ET	Early Termination
g	Gram
GCP	Good Clinical Practice
Н	Hours
HIV	Human Immunodeficiency Virus
HPV	Human Papilloma Virus
ICH	International Conference on Harmonization
IWRS	Interactive Web Response System
LOCF	Last Observation Carried Forward
MedDRA	Medical Dictionary of Regulatory Activities
mITT	Modified Intent-To-Treat
PD	Protocol Deviation
PI	Principal Investigator
РР	Per-Protocol
PV	Protocol Violation
PVPD	Protocol Violation and Protocol Deviation
RLD	Referenced Listed Drug
SAE	Serious Adverse Event
SD	Standard Deviation

Confidential

TEAETreatment Emergent Adverse EventUPTUrine Pregnancy TestWHOWorld Health Organization

3 INTRODUCTION

This document describes the statistical methods and data presentations to be used in the summary and analysis of data from Protocol 016-POD-001 version 2.0 dated 15Jan2018. Background information is provided for the overall study design and objectives. The reader is referred to the study protocol and electronic case report forms (eCRFs) for details of study conduct and data collection.

3.1 Study Overview

Clinical study of protocol 016-POD-001 is a multicenter, parallel group, randomized, doubleblind, placebo-controlled, trial with clinical endpoint comparing Podofilox Topical Gel 0.5% to Condylox[®] Gel 0.5% and a matching placebo. The study will be conducted in adult male and female patients with external anogenital warts. The study also assesses comparative safety of Podofilox Topical Gel 0.5% and Condylox[®] Gel 0.5%.

Safety data analysis will include local application site reaction scores (erythema, dryness, burning/stinging, erosion, edema, pain, itching and bleeding), reported adverse events, vital signs and concomitant medication assessments summarized by treatment group and time point of collection, when appropriate.

The primary objective is to compare the clinical efficacy among patients with anogenital warts when treated with Podofilox Topical Gel 0.5% versus Condylox[®] Gel 0.5% and placebo. The secondary objective is to demonstrate safety of Podofilox Topical Gel 0.5% compared to Condylox[®] Gel 0.5% and placebo assessed by the frequency and severity of adverse events, and application site reaction scores (erythema, dryness, burning/stinging, erosion, edema, pain, itching, and bleeding).

The planned overall sample size for this clinical trial is approximately 413 adult male and female patients with external anogenital warts, who will be randomized at a 3:3:1 ratio (test: RLD: placebo) at about 16 clinical research centers in the United States, Russia and Ukraine. The mITT and PP population sizes will be approximately 392 and 350, correspondingly. A subject is considered enrolled after he/she has provided a signed informed consent and begins the screening process. A subject is considered randomized upon receiving his/her randomized treatment assignment.

Confidential

The entire study will consist of a maximum of 6 visits:

- 1. Visit 1 (Day -14 up to -1): Screening Evaluations at the Study Site performed.
- 2. Visit 2 (Day 0): Study Drug Dispensation.
- 3. Visit 3-5 (Day 7 ±1 [Week 1], Day 14 ±1 [Week 2], and Day 21 ±1 [Week 3]: Follow-up of the Study Drugs.
- 4. Visit 6 (Day 28 ± 5 [Week 4]): End of Study Visit / Early Termination Visit at the Study Site including Safety and Efficacy Evaluation.

3.2 Schedule of Events

Table 2.2.1 Study visits and assessments.

	Screening Visit 1	Baseline Visit 2	Treatment Period			
Study Visit			Visit 3	Visit 4	Visit 5	EOS/ET Visit 6
Visit Day	Day -14 to -1	Day 0	Day 7 (±1)	Day 14 (±1)	Day 21 (±1)	Day 28 (±5)
Informed Consent	Х					
Subject Demographics	Х					
Medical History	Х					
Concomitant and Prohibited Therapies Review	Х	Х	Х	Х	Х	Х
Vital Signs	Х	Х	Х	Х	Х	Х
Physical Examination	Х	Х				Х
Visual Inspection of EAWs ¹	Х	Х	Х	Х	Х	Х
Serology test for HIV ²	Х					
Test for Hepatitis B, C	Х					
Test for Syphilis ³	Х					
Urine Pregnancy Test	Х	Х				Х
Eligibility Criteria Check	Х	Х				
Randomization		Х				
Training on Study Drug Application		Х				
Training on Subject Diary Card Completion and Contraception Methods		Х				
Study Drug Dispensation		Х	Х	Х	Х	
Assessment of Local Application Site Reactions		Х	Х	X	Х	Х
Adverse Events Assessment	Х	Х	Х	Х	Х	Х
Study Drug Return and Accountability			Х	X	X	X
Subject Diary Card Return and Review			X	X	X	X

Protocol: 16-POD-001 Version 2.0, 15-Jan-2018

Confidential

Subject Diary Card Dispensation		Х	Х	Х	Х	
Histological Confirmation of Diagnosis ⁴	Х					

¹ If total disappearance of all warts is achieved within all treated areas at visits 2, 3, 4, or 5, respective visit will be considered an End of Study (EOS) visit. In the case where reduction of warts is absent or incomplete, a new treatment cycle will be initiated for a maximum of four cycles in total for the subject.

² Test may not be repeated if the subject has negative HIV test results within 4 weeks before baseline. Copy of the test result needs to be filed with the study records.

³ If required by applicable local regulations.

⁴ Histological confirmation will be obtained if there is any doubt of the diagnosis.

4 STUDY OBJECTIVE AND ENDPOINTS

4.1 Study Objectives

The primary objective of this study is:

• To compare the clinical efficacy of anogenital warts treatment of patients treated with Podofilox Topical Gel 0.5% and patients treated with Condylox® Gel 0.5% to patients treated with placebo (superiority comparisons), and to compare efficacy of Podofilox Topical Gel 0.5% with that of Condylox[®] Gel 0.5% (bioequivalence comparison).

The secondary objective of this study is:

• To demonstrate safety of Podofilox Topical Gel 0.5% compared to Condylox[®] Gel 0.5% or placebo assessed by the frequency and severity of adverse events and application site reaction scores (erythema, dryness, burning/stinging, erosion, edema, pain, itching and bleeding).

4.2 Study Endpoints

4.2.1 Primary Endpoint

The primary endpoint is the proportion of subjects who achieve complete cure within the follow up period. The proportion of subjects with complete cure for Podofilox Topical Gel 0.5% will be compared with that of Condylox[®] Gel 0.5% using an equivalence analysis. For superiority analysis, each active treatment will be compared with Placebo.

4.2.2 Secondary (Safety) Endpoints

Adverse events will be summarized by frequency, by severity and will be tabulated by body system/organ class.

Confidential

Local application site reactions scores (erythema, dryness, burning/stinging, erosion, edema, pain, itching and bleeding) in each group during the study drug application period will be summarized by type of reaction and by intensity score.

5 STUDY DESIGN

5.1 Summary of Study Design

This is a multicenter, parallel group, randomized, double-blind, placebo-controlled trial with clinical endpoint comparing Podofilox Topical Gel 0.5% to Condylox[®] Gel 0.5% and a matching placebo. The study will be conducted among adult male and female patients with external anogenital warts.

On the following day after the Baseline visit (Day 1) the subject will apply the study drug on EAWs following the recommendations given during training at the clinic site. The treatment phase will consist of four weekly treatment cycles at a maximum, during which the drug will be applied twice a day (in the morning and at the bedtime) for 3 consecutive days, then discontinuing for 4 consecutive days. Study drug will thus be applied only on Days 1, 2, 3, 8, 9, 10, 15, 16, 17, 22, 23 and 24.

Study visits will occur on the seventh (7) day of each treatment cycle: on Day 7 (Week 1), Day 14 (Week 2), Day 21 (Week 3), and Day 28 (Week 4). Primary endpoint (total disappearance of all treated warts) will be evaluated during each of these visits. In case the primary endpoint is reached at any of the visits prior to the Day 28 visit, it will be considered the End of Study (EOS) visit – the Investigator will perform physical examination and repeat urine pregnancy test, and subject's participation will be considered complete. If total disappearance of warts is not achieved, a new treatment cycle will be initiated for a maximum of four cycles in total for the subject.

During each study visit, the Investigator will collect vital signs, evaluate EAWs for absence or presence, capturing the count of EAWs, record Local Application Site Reactions and adverse events (AEs), assess Patient's Diary Card completion and subject's compliance with the study drug application, review concomitant medication and confirm that there were no prohibited therapies applied since the last visit.

In the event the primary endpoint (total disappearance of all warts within all treated areas) has been achieved prior to the Day 28 visit, this visit will be considered End of Study (EOS) visit. In case a subject discontinues prematurely, the Investigator will conduct an Early Termination (ET) visit, capturing the reason for discontinuation and performing assessments of EOS visit.

Protocol: 16-POD-001 Version 2.0, 15-Jan-2018

Confidential

5.2 Definition of Study Drugs

- Arm 1 (Test product): Subjects in this arm will receive test formulation of Podofilox Topical Gel 0.5% (Hyloris Developments SA).
- Arm 2 (Reference Listed Drug [RLD]): Subjects in this arm will receive RLD Condylox[®] Gel 0.5% (Allergan Pharmaceuticals).
- Arm 3 (Placebo): Subjects in this arm will receive a vehicle that matches the test product, except for the inclusion of the active ingredient (Hyloris Developments SA).

5.3 Sample Size Considerations

Approximately 413 subjects (177 in each active arm and 59 in placebo group) will be enrolled to obtain at least 392 mITT subjects (168 in each active treatment arm and 56 in placebo group) and to complete 350 PP subjects (150 in each active arm and 50 in placebo group). This sample size was calculated assuming that both active treatments would have equivalent success rates of 40% and placebo would have a success rate of 15%. This sample size will provide an overall probability of at least 0.9 of having the 90% Wald confidence interval, with Yates' continuity correction, of the difference between the test and reference success rates contained within the interval -0.20 to +0.20 in the PP population, in addition to establishing that the success rates for both active treatments are statistically greater than that of the placebo arm (two-sided continuity-corrected Z-tests, $\alpha = 0.05$) in the mITT population.

mITT (T:R:Placebo)	Prob. of Superiority*	of Superiority* PP (T:R:Placebo) Prob.		Prob. of study success
168:168:56 (392)	0.98	150:150:50 (350)	0.92	0.90

*) Superiority analysis based on two-sided, α = 0.05, continuity-corrected Z-tests.

**) Bioequivalence (BE) analysis based on 90% confidence interval (CI) of the difference between Test and reference for proportions of subjects with treatment success, calculated by the Wald's method with Yates' continuity correction.

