7.5 Analysis Populations

7.5.1 Definitive and Supplemetal

Due to GCP non-compliance at site 201, it was decided to exclude data from that site from the Definitive Efficacy Analysis. A Supplemental Efficacy Analysis will be presented including the data from site 201.

The mITT and PP populations defined below will not inlcude site 201. However, there will be a supplemental mITT population (mITTs) and a supplemental PP population (PPs), both of which will include site 201.

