9.1.1 Bioequivalence Analysis

The efficacy bioequivalence of the test and reference treatments will be based on the proportions of subjects with clinical success. The hypothesis tested for clinical equivalence between test and reference will be:

Bioequivalence between the test and the reference product will be established if the 90% confidence interval for the difference in success proportions is contained within the equivalence limits [-0.20, +0.20].

In this case, the compound hypothesis to be tested is:

 $H_0: P_T - P_R < -0.2$ or $P_T - P_R > 0.2$ (meaning test product is not bioequivalent to the reference);

versus

 $H_a: -0.2 \leq P_T - P_R \leq 0.2$ (supporting bioequivalence);

where P_T = success proportion of test treatment, P_R = success proportion of reference treatment.

Let

- 1. n_T = sample size of test treatment group
- 2. $cn_T =$ number of subjects with success in test treatment group
- 3. n_R = sample size of reference treatment group
- 4. $cn_R =$ number of subjects with success in reference treatment group

$$\hat{P}_T = {cn_T / n_T}, \ \hat{P}_R = {cn_R / n_R},$$

Confidential

and
$$se = \left(\frac{\hat{P}_R(1 - \hat{P}_R)}{n_R} + \frac{\hat{P}_T(1 - \hat{P}_T)}{n_T} \right)^{1/2}$$

The 90% confidence interval will be estimated using Wald's method with Yates' continuity correction, as:

$$L = (\hat{p}_{T} - \hat{p}_{R}) - 1.645 \text{ se} - (1/n_{T} + 1/n_{R})/2$$
$$U = (\hat{p}_{T} - \hat{p}_{R}) + 1.645 \text{ se} + (1/n_{T} + 1/n_{R})/2$$

 H_0 will be rejected if $L \geq$ -0.20 and $U \leq 0.20$ resulting in accepting H_A and concluding bioequivalence of the two products.

Tthe following SAS code will be used to test bioequivalence:

```
proc freq data = dataset;
tables treat*outcome/ riskdiff (Equiv correct);
run;
```

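### SAP 5.3 and 3.1 keep the all-sites sizes of 392 mITT and 350 PP, and 5.3 keeps its overall probability of at least 0.9, although site 201 is now excluded from both sets

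*SAP*

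**What the plan says.** SAP 5.3 sets the planned enrolment and the mITT target: "Approximately 413 subjects (177 in each active arm and 59 in placebo group) will be enrolled to obtain at least 392 mITT subjects", split 168:168:56. For the per-protocol set the aim is "to complete 350 PP subjects (150 in each active arm and 50 in placebo group". The words 'at least' belong to the mITT figure only. SAP 3.1 repeats both sizes as approximate: "The mITT and PP population sizes will be approximately 392 and 350, correspondingly". The SAP synopsis repeats them too.

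SAP 5.3 assumes 40% success on each active and 15% on placebo. It then states: "This sample size will provide an overall probability of at least 0.9 of having the 90% Wald confidence interval, with Yates' continuity correction" lying within ±0.20 in PP, together with superiority of both actives to placebo in mITT. Its table gives 0.98 for superiority, 0.92 for equivalence and 0.90 for study success.

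SAP 7.5.1 says: "The mITT and PP populations defined below will not inlcude site 201". Site 201 stays only in the supplemental sets, mITTs and PPs. SAP 6 and 9.1 make the analysis without site 201 the definitive one. SAP 6 cites a note to file dated 27 Feb 2019, so the exclusion was known when this text was written.

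Neither document gives site 201's subject count, the actual enrolment, or any replacement of its subjects.

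**The concern.** The terms mITT and PP now carry sizes planned with every site included and definitions that remove one site. The probabilities in SAP 5.3 were worked out at the all-sites sizes, while the definitive equivalence and superiority tests will run on the reduced sets.

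A reader of the SAP therefore cannot tell what size, or what chance of success, the definitive tests were expected to have. The overall figure is also worded as a minimum of 0.9. If that minimum is only just met at full planned size, any net loss of subjects makes the sentence untrue.

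**Working it through.** **Inputs.** From SAP 5.3: success rates 0.40, 0.40 and 0.15; mITT 168:168:56; PP 150:150:50; two-sided α = 0.05 with continuity-corrected Z-tests. From SAP 9.1.1: margin ±0.20 and the interval, difference ± 1.645 se ± (1/n_T + 1/n_R)/2. From SAP 3.1: about 413 randomised at about 16 centres. Assumed, because the documents do not say: the fraction f of subjects at site 201, proportional loss across arms, and no replacement.

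**1. Equivalence at planned size, n = 150 per arm.** With equal true rates and equal arms, the normal approximation is

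P = 2Φ[(0.20 − 1/n)/√(2 × 0.4 × 0.6/n) − 1.645] − 1.

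Here √(0.48/150) = 0.0566 and (0.20 − 0.0067)/0.0566 = 3.418. So P = 2Φ(1.773) − 1 = 0.924. Exact binomial enumeration of the SAP interval gives 0.928. The SAP states 0.92.

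**2. Superiority at planned size, 168 against 56, one active.** The unpooled se is √(0.24/168 + 0.1275/56) = 0.0609. The correction is (1/168 + 1/56)/2 = 0.0119. Then Φ[(0.25 − 0.0119)/0.0609 − 1.960] = Φ(1.951) = 0.975. Without the correction it is 0.984. The SAP states 0.98.

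**3. Overall.** 0.975 × 0.924 = 0.900, and the SAP states 0.90. The SAP's figures are thus reproduced closely by one active-versus-placebo comparison multiplied by equivalence. On that basis the 0.9 minimum has no slack.

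**4. Enrolment allowance.** 413 − 392 = 21 subjects. An average site is 413/16 ≈ 26, and 413 − 26 = 387, which is below 392 before any attrition.

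**5. Removing site 201.** Each arm is scaled by (1 − f) and steps 1 to 3 are repeated:

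| Assumed loss | mITT active:placebo (total) | PP per active arm (total) | Equivalence | Superiority, one active | Product |
|---|---|---|---|---|---|
| none | 168:56 (392) | 150 (350) | 0.924 | 0.975 | 0.900 |
| 5% | 160:53 (373) | 142 (332) | 0.906 | 0.967 | 0.876 |
| 1/16, about 26 subjects | 158:52 (368) | 141 (329) | 0.903 | 0.964 | 0.871 |
| 10% | 151:50 (352) | 135 (315) | 0.887 | 0.957 | 0.849 |
| 20% | 134:45 (313) | 120 (280) | 0.834 | 0.933 | 0.778 |

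Exact equivalence values for 141 and 120 per arm are 0.901 and 0.835, so the approximation is adequate. By the approximation, equivalence stays at or above 0.90 down to 140 PP subjects per active arm, and at or above 0.85 down to 124.

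**6. A separate matter at full planned size.** SAP 5.3 and 9.1.2 require both actives to beat placebo. Exact enumeration of both comparisons (unpooled, corrected, shared placebo arm) gives 0.933 at 168:168:56; the normal approximation gives 0.956. Neither is 0.98. With PP nested in mITT, simulation puts the overall probability at about 0.87 with every site included. None of this gap comes from site 201.

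**The case against.** The strongest reply is that no shortfall has been shown. A reader might infer that the definitive sets are smaller than 392 and 350. The documents do not establish this: they give neither site 201's count nor actual enrolment, 413 is itself approximate, and over-enrolment, replacement or lower attrition could offset the loss. Silence on replacement is not evidence that there was none. This stands, and it is why the point is conditional.

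A reader might also infer that 392 and 350 now describe mITTs and PPs. That would need about 413 enrolled with site 201 counted and attrition as planned, which is unknown.

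The consequence can be overstated as well. For an average-sized site the equivalence probability is still about 0.90, above the 85% in Protocol 8.2 Table 5. The margin, interval, α and decision rules are unchanged. The planned placebo arm is small, but under proportional loss it goes from 56 to 52 and is not singled out.

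Finally, SAP Appendix A plans disposition tables by site and with and without site 201, and SAP 7.5.3 settles population membership at a meeting before database lock. Actual counts will therefore be reported, and final PP counts may not exist when the SAP is signed. That limits what 5.3 can state to expected sizes. It does not explain why 5.3 and 3.1 give superseded figures without saying so.

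**Conclusion.** The inconsistency is real and rests on the SAP's text alone: 5.3 and 3.1 were not reconciled with 6, 7.5.1 and 9.1. Unless enrolment made up for site 201, the definitive sets will be smaller than the sizes behind 0.98, 0.92 and 0.90, and the 0.9 minimum will not hold.

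The size depends on an unknown. With 413 enrolled, proportional loss and no replacement, one average site takes equivalence from about 0.92 to 0.90 and the overall probability from 0.90 to about 0.87; a 20% loss takes them to about 0.83 and 0.78. With full replacement nothing changes. Proportional loss is an assumption too, since Protocol 5.5 names gender, not site, as the stratification factor.

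This is a reporting and reconciliation defect. It does not show that the trial is underpowered. The both-arm superiority figure of about 0.93 against the stated 0.98 should be corrected in the same edit, but it must not be counted as an effect of excluding site 201.

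**What to change.** - In SAP 5.3 and 3.1, and where the synopsis repeats them, mark 392 and 350 as the original all-sites plan. In 5.3, mark their probabilities the same way.
- State the expected mITT and PP sizes without site 201 from a blinded count, and say whether replacements were enrolled, with the revised enrolment figure if so.
- Restate the equivalence, both-arm superiority and overall probabilities at those sizes, and say which superiority calculation was used.
- Do not relabel 392 and 350 as the mITTs and PPs sizes unless the counts support it.

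The cost is SAP wording, one blinded subject count and a short recalculation. No analysis, margin or decision rule changes. The restated overall probability will probably be lower than 0.90, partly because of the both-arm requirement and regardless of site 201.

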1.2.2 Clinical Experience

Following data is available for RLD Condylox® Gel 0.5% clinical trials.

In the first multicenter clinical study in 326 patients with anogenital warts, Condylox® Gel 0.5% and its vehicle were applied in a double-blind fashion to comparable patient groups. ¹³ Of the 260 patients with efficacy data, 176 were treated with Condylox® Gel 0.5%. Patients applied Condylox® Gel 0.5% twice daily for three consecutive days followed by a 4 day "rest" period. At the end of 4 weeks, 38.4% of the patients had complete clearing of the wart tissue when treated with Condylox® Gel 0.5%.

In the second multicenter clinical trial in 108 evaluable patients with anogenital warts, Condylox® (podofilox) Topical Solution 0.5% was compared with Condylox® Gel 0.5% for efficacy. As in the first clinical trial, patients applied Condylox® Gel 0.5% twice daily for three consecutive days followed by a four day "rest" period. Similar clearance rates were observed. At the end of 4 weeks, 25.6% of the patients had complete clearing of the wart tissue when treated with Condylox® Gel 0.5%. ¹⁴

Confidential Page 22 of 59

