8.2 Sample Size Determination

The difference in the proportion of subjects in the test and reference treatment groups who achieve "treatment success" defined as "total disappearance of all warts within all treated areas" at four days (\pm 5 days) after the last day of the last cycle of treatment will be evaluated using a two-sided 90% confidence interval. The therapeutic equivalence of the test and reference products will be established if the confidence bounds of the 90% confidence interval are contained within the limits of -0.20 to +0.20. The results in the PP population will be considered definitive for therapeutic equivalence with those in the mITT population considered supportive.

Table 5. Sample Size Rationale

Equivalency margin	Power (%)	CI (%)	Sample Size mITT* (test: RLD: placebo)	Sample Size PP* (test: RLD: placebo)	
20%	85%	90%	392 (168:168:56)	350 (150:150:50)	

^{*} Sample sizes were calculated assuming: 40.0% success rate for active treatment, and 15.0% success rate for vehicle; 20% equivalency margin (EQ).

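### The success probability of at least 0.9 in SAP 5.3 is not reached at its own 40%/15% rates when both superiority tests are required, and the lower reference-gel rates in Protocol 1.2.2 widen the gap

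*SAP*

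**What the plan says.** SAP 5.3 plans 168:168:56 mITT subjects and 150:150:50 PP subjects (test, reference, placebo). It names the rates behind these numbers: "This sample size was calculated assuming that both active treatments would have equivalent success rates of 40% and placebo would have a success rate of" (the figure given is 15%). The claim that follows is: "This sample size will provide an overall probability of at least 0.9". The event described is that the continuity-corrected 90% Wald interval for test minus reference lies within ±0.20 in the PP population, and that both actives are significantly above placebo in the mITT population (two-sided continuity-corrected Z-tests, 0.05). The accompanying table gives 0.98 for superiority, 0.92 for bioequivalence and 0.90 for study success.

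Protocol 8.2 uses the same rates ("40.0% success rate for active treatment, and 15.0% success rate for vehicle") and the same sample sizes, but Table 5 states 85% power.

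Protocol 1.2.2 reports two trials of the reference gel on the same weekly schedule. In the first, with 176 gel patients among those with efficacy data: "At the end of 4 weeks, 38.4% of the patients had complete clearing of the wart tissue". In the second, with 108 evaluable patients over the gel and solution arms together: "At the end of 4 weeks, 25.6% of the patients had complete clearing of the wart tissue when treated with Condylox® Gel 0.5"%. The first trial had a vehicle arm, but its clearance rate is not quoted. Neither document gives a source for 40% or 15%, or shows how the probability changes at other rates.

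**The concern.** The reference product is the gel whose cited rates are 38.4% and 25.6%, yet the sizing uses 40% for both actives. A lower active rate slightly helps the equivalence interval, because the variance falls, but it shrinks the gap to a placebo arm of only 56. Someone checking equivalence alone would not see the loss.

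The table entries raise a second doubt. Requiring both actives to beat a shared placebo arm is harder than requiring one, and 0.98 looks high for both.

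At stake is whether readers of the plan have a true picture of the chance that the trial meets all its criteria. Equivalence without superiority of both actives over placebo is harder to interpret.

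**Working it through.** **Inputs.** Active rates of 40% (SAP 5.3), 38.4% and 25.6% (Protocol 1.2.2), with test equal to reference. Vehicle 15% (SAP 5.3). Superiority on 168 per active and 56 placebo; equivalence on 150 per active. Applying the same rates to the PP and mITT populations is an assumption.

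**Reproducing the plan's figures (normal approximation, unpooled SE, 40%/15%).**

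- Equivalence: se = √(2 × 0.40 × 0.60/150) = 0.0566. Probability = 2Φ((0.20 − 1/150)/0.0566 − 1.645) − 1 = 2Φ(1.773) − 1 = 0.924. Stated: 0.92.
- One active against placebo: se = √(0.24/168 + 0.1275/56) = 0.0609; correction = (1/168 + 1/56)/2 = 0.0119. Probability = Φ((0.25 − 0.0119)/0.0609 − 1.96) = Φ(1.951) = 0.974; without the correction, 0.984. Stated: 0.98.
- Product: 0.924 × 0.974 = 0.900. Stated: 0.90.

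The table is thus recovered, to within rounding, by counting **one** active-versus-placebo comparison. Requiring both in the same approximation gives 0.956 for superiority and 0.889 jointly.

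**The event as SAP 5.3 describes it.** The components come from exact binomial enumeration. The joint probability comes from simulation (400,000 to 1,000,000 trials), with a shared placebo arm and the PP population nested in the mITT population. An active is superior if (p̂A − p̂P − (1/nA + 1/nP)/2)/se ≥ 1.96. SAP 9.1.2 calls the formulation similar to the equivalence one, whose SE is unpooled, so the unpooled figure is the closer reading. Cells show unpooled / pooled.

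| Active rate (vehicle 15%) | One active superior | Both superior | BE | Joint |
|---|---|---|---|---|
| 40% | 0.96 / 0.94 | 0.93 / 0.91 | 0.93 | 0.87 / 0.85 |
| 38.4% | 0.93 / 0.91 | 0.90 / 0.86 | 0.93 | 0.85 / 0.81 |
| 25.6% | 0.39 / 0.29 | 0.28 / 0.19 | 0.97 | 0.27 / 0.19 |

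With 15% vehicle, the joint comes to about 0.90 only when the active rate is near 45% (0.900 / 0.895). The one-comparison shortcut that returns 0.900 at 40% gives 0.886 at 38.4% and 0.35 at 25.6%.

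**Dependence on the vehicle rate (joint, unpooled / pooled).**

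| Active rate | Vehicle 15% | 10% | 5% |
|---|---|---|---|
| 38.4% | 0.85 / 0.81 | 0.93 / 0.92 | 0.93 / 0.93 |
| 25.6% | 0.27 / 0.19 | 0.65 / 0.54 | 0.94 / 0.91 |

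At 38.4%, 0.9 is regained at a vehicle rate of about 11 to 12%; at 25.6%, at about 5 to 6%.

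**Neither active superior (vehicle 15%)**, from 1 − 2 × P(one) + P(both). At 38.4%: 1 − 2 × 0.9348 + 0.8992 = 0.03 unpooled and 1 − 2 × 0.908 + 0.8589 = 0.04 pooled. At 25.6%: 1 − 2 × 0.3853 + 0.2755 = 0.50 and 1 − 2 × 0.2893 + 0.1914 = 0.61.

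**The case against.** Several points on the other side stand.

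- A reader might infer that SAP 5.3 promises 0.9 whatever the rates. It does not: the sentence just before the claim states the 40% and 15%, and the lower rates are printed openly in the protocol.
- A reader might blame the whole shortfall on an optimistic 40%. At 38.4% the rate accounts for only 2 to 4 points; the rest of the gap to 0.90 is there at 40%. The first trial's 38.4% on 176 patients has a 95% interval of 0.384 ± 1.96 × √(0.384 × 0.616/176), about 31% to 46%, so 40% is compatible with it. Only the 25.6% trial implies a large loss.
- The vehicle rate is as unsourced as the active rate, and a lower one restores 0.9. Varying only the active rate would mislead.
- The miss at 40% is modest, and some variants reach 0.9. Two-sided tests without the correction give a joint of 0.902 by normal approximation. One-sided 0.05 tests without it give 0.903 to 0.909, and with it 0.888 to 0.898. But SAP 5.3 specifies two-sided, corrected tests.
- A reader might infer that failing the superiority requirement means the trial cannot show that either gel works. The documents do not support that: SAP Table 14.2.3.1.1 reports each active against placebo separately, and at 38.4%/15% the chance that neither is superior is only 0.03 to 0.04.

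Narrower eligibility, or counting clearance at any visit, might lift the true rate above the cited ones, but neither document argues this.

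**Conclusion.** The stated probability of at least 0.9 is wrong for the event that SAP 5.3 describes. At the plan's own 40%/15% it is about 0.85 to 0.87 (0.889 by normal approximation), because the 0.98 corresponds to one comparison with placebo rather than two. At the cited reference-gel rates, with 15% vehicle, it falls to 0.81 to 0.85 and to 0.19 to 0.27. Equivalence is adequately powered throughout (0.93 to 0.97); the whole further loss is in superiority.

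These figures assume equal test and reference rates, the planned population sizes, the same rates in both populations and, for the headline values, 15% on vehicle. The size at the cited rates is therefore conditional on an unsourced vehicle rate; the miss at 40%/15% rests on the plan's own inputs.

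The protocol's 85% for the same sample sizes agrees with the pooled joint figure of 0.85. A reader might conclude that the protocol has the right number and the SAP a slip, but Table 5 does not say which event its 85% refers to, so the two need reconciling rather than one being preferred.

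**What to change.** Keep the sample size and the tests. In SAP 5.3:

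- replace the claim of at least 0.9, and the 0.98 and 0.90 table entries, with the recomputed probabilities at 40%/15%, stating that superiority means both actives and which SE the Z-test uses;
- add a short table over active rates of 40%, 38.4% and 25.6% and vehicle rates of 5%, 10% and 15%, with columns for both superior (mITT), BE (PP) and joint;
- give the source of the 40% and the 15%, or label them as planning assumptions, and acknowledge the two rates in Protocol 1.2.2;
- say what the 85% in Protocol Table 5 refers to and reconcile it with the SAP figure.

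A row for a pooled cited rate is optional, because the number of gel patients in the second trial is not given. The cost is wording and one small table, with no extra patients and no change to conduct or analysis. The downside is a less favourable stated probability.
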